1. REPORTING & ANALYSIS PLAN SYNOPSIS

Overview	Key Elements of the RAP
Purpose	The purpose of this reporting and analysis plan (RAP) is to describe: 
 Planned analyses and output for the final data.
Protocol	
 This RAP is based on Protocol Amendment 1(Dated: 05/JAN/2017) of study 202062 (GlaxoSmithKline Document Number 2016N288743_01)
Primary Objective	
 To assess the safety and tolerability of single and repeat doses of GSK2292767 as a dry powder in healthy cigarette smokers.
Primary Endpoint	
 Safety and tolerability of GSK2292767 as assessed by clinical monitoring of: 
 Vital Signs Spirometry Electrocardiogram (ECG) Laboratory safety data Adverse events (AEs)
Study Design	
 This is a two part, single site, randomised, double-blind (sponsor open), placebo controlled study in healthy smokers. Part A will consist of two 3-period interlocking cohorts. Part B is planned to follow Part A and is a parallel group design. The highest well tolerated dose achieved in Part A will be selected for Part B.
Planned Analyses	
 All decisions regarding final analysis, as defined in this RAP document, will be made prior to Database Freeze (unblinding) of the study data.
Primary Analysis Population	
 Primary: Safety Population (Comprised of subjects who receive at least one dose of study treatment and will be based on the treatment which the subject actually received).
Estimation	
 An estimation and inference approach will be adopted to evaluate the objectives.
Primary Analyses	
 Safety data will be presented in tabular and/or graphical format and summarised descriptively according to GSK's Integrated Data Standards Library (IDSL) standards.

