
 • The PK parameter will be dose-normalised prior to log_e-transformation by multiplying by reference dose / dose • Dose will be fitted as a fixed effect, subject as a random effect using DDFM=KR. • Separate lines will be fitted for each cohort by including terms for cohort and cohort*log_e(dose). If the slopes are not significantly (p-value<0.05) different from each other, the interaction term will be removed and a single slope estimate obtained. If the slopes are significantly different from each other, a separate slope estimate and associated 90% confidence interval will be reported for each cohort. • The reference dose will be chosen based on the lowest clinically relevant dose over which PK can be adequately described, with each other dose as the test doses in the construction of the ratio $\mu(\text{test})/\mu(\text{reference})$.
Model Checking & Diagnostics

 • Refer to Appendix 8: Model Checking and Diagnostics for Statistical Analyses.
Model Results Presentation

 • Point estimates for the adjusted means on the log_e scale, the mean difference between each dose (test) and the reference dose and associated 90% confidence interval will be constructed using the residual variance. These will not be presented. • The point estimate and confidence interval will then be exponentially back-transformed to allow the presentation of the adjusted (least square) geometric means for each treatment (dose), and point estimates and associated 90% confidence intervals for the ratio test/reference. • Point estimates and 90% confidence intervals for AUC, C_{max} and C_τ will be reported to 2 decimal places Treatment ratios and 90% CIs will be plotted by dose. • Plots will also be provided showing the adjusted geometric mean ratio of test to reference treatment (dose) for AUC(0-∞), AUC(0-t), C_τ and C_{max} together with 90% confidence interval.

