8.2.2. Planned Pharmacodynamic Statistical Analyses

Planned Statistical Analyses
Endpoint(s)

 • PIP3 Peak Area proportion (calculated as a proportion of the sum of PIP2 Peak Area and PIP3 Peak Area i.e. $\text{PIP3 Peak Area} / (\text{PIP2 Peak Area} + \text{PIP3 Peak Area})$)
Model Specification

 • Repeated measures analysis based on the two replicates for each subject on each study day. • Replicates are to be modeled using VC (variance components) structure • Response variable: $\text{Loge}(\text{PIP3 Peak Area proportion})$. The following will be included as fixed effects: Part A: period, treatment*daytime Part B: treatment*daytime*base Where daytime can take the values: Part A: 'Day 1 3h', 'Day 1 24h' Part B: 'Baseline', 'Day 1 3h', 'Day 1 24h', 'Day 12 3h', 'Day 12 24h' • Daytime and subject will be fitted as random effects
Model Checking

 • Refer to Appendix 8: Model Checking and Diagnostics for Statistical Analyses.

Planned Statistical Analyses
Model Results Presentation

• Adjusted geometric means for each treatment group will be presented along with 90% confidence intervals (CIs).• Part A: Point estimates of the treatment differences versus placebo and their associated 90% CIs will be calculated for both timepoints (using the pooled estimate of variance) and back transformed to provide estimates and 90% CIs for the treatment ratios.• Part B: Point estimates of the daytime differences versus placebo and their associated 90% CIs will be calculated (using the pooled estimate of variance) and back transformed to provide estimates and 90% CIs for the treatment ratios at each timepoint.• Bayesian posterior probabilities of seeing differences from placebo less than 0 (ratio less than 1) will be displayed.• Adjusted geometric means (for each treatment group and timepoint) and treatment ratios, along with 90% CIs will be plotted.

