10.4. Appendix 4: Data Display Standards & Handling Conventions

10.4.1. Study Treatment & Sub-group Display Descriptors

Treatment Group Descriptions			
RandAll NG		Data Displays for Reporting	
Code	Description	Description ^[2]	Order ^[1]
A	Placebo inhaled single dose	Placebo	1
B	50ug GSK2292767 inhaled single dose	50ug OD	2
C	Dose Level 2 GSK2292767 inhaled single dose	100ug OD	3
D	Dose Level 3 GSK2292767 inhaled single dose	200ug OD	4
E	Dose Level 4 GSK2292767 inhaled single dose	500ug OD	5
F	Dose Level 5 GSK2292767 inhaled single dose	1000ug OD	6
G	Dose Level 6 GSK2292767 inhaled single dose	2000ug OD	7
H	Placebo inhaled repeat dose	Placebo	1
I	Dose Level 7 GSK2292767 inhaled repeat dose	XXXXug OD	2

NOTES:

1. Order represents treatments being presented in TFL, as appropriate.
2. Replace X's with the actual agreed dose for the cohort and period.

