10.4.2. Baseline Definition & Derivations

10.4.2.1. Baseline Definitions

For all endpoints the baseline value will be the latest pre-dose assessment. For Part A, baseline definitions are applicable to each period. Note that no baseline sputum assessments are planned for Part A so any comparisons will be purely versus placebo at the corresponding timepoints.

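### The Part A PIP3 model has no cohort term, so if the two cohorts differ systematically, part of that difference enters the dose-placebo ratios with opposite sign for the two cohorts' doses

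*SAP*

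**What the plan says.** The SAP synopsis (section 1) states: "Part A will consist of two 3-period interlocking cohorts". Section 10.4.1 lists six single-dose active levels (50 to 2000 µg) and one Part A placebo code, "Placebo inhaled single dose". Its table note says the dose shown is the one agreed for the cohort and period.

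Section 8.2.2 specifies the PIP3 analysis:
- Data: "Repeated measures analysis based on the two replicates for each subject on each study day".
- Fixed effects: "Part A: period, treatment*daytime", with daytime taking the values 3h and 24h on Day 1.
- Random effects: "Daytime and subject will be fitted as random effects".
- Reported contrast: "Part A: Point estimates of the treatment differences versus placebo and their associated 90% CIs will be calculated for both timepoints". Posterior probabilities of a ratio below 1 are reported as well.

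Section 10.4.2.1 adds: "Note that no baseline sputum assessments are planned for Part A so any comparisons will be purely versus placebo at the corresponding timepoints".

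Cohort does appear elsewhere. For Part A dose proportionality, section 8.1.5.1 says, under the ANOVA method: "Separate lines will be fitted for each cohort by including terms for cohort and cohort*log_e(dose" (the closing bracket follows). For Part B PK, section 8.1.6 adds cohort as a covariate if there is more than one cohort.

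The SAP does not state which cohort receives which dose level, whether every subject has a placebo period, or whether period is coded 1 to 3 in both cohorts or as six cohort-specific sessions.

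**The concern.** Each active dose is given in one cohort, but its comparator is placebo pooled over both. With subject random, the mixed model combines within-subject and between-subject information, so each dose is compared partly with the other cohort's placebo subjects. A systematic difference between cohorts in PIP3 level would therefore leak into every contrast. Part A has no baseline sputum sample, so nothing else in the model can take it out.

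What is at stake is the dose-response picture for the biomarker. The error has one sign for one cohort's doses and the opposite sign for the other's, so it could distort the pattern across doses as well as its level. The ratios, their 90% CIs and the posterior probabilities would all carry it.

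**Working it through.** The SAP gives no PIP3 sample size, variance or cohort difference, so there is no planned figure to reproduce. The check takes the expectation of the generalised least squares estimate under the planned model when one cohort is shifted by D on the log scale.

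**From the SAP:** two cohorts, three periods, one placebo code, fixed effects period and treatment*daytime, random subject, two timepoints and two replicates.

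**Assumed:**
- Period is coded 1 to 3 in both cohorts, and the cohorts are of equal size.
- Doses 1, 3, 5 go to one cohort and 2, 4, 6 to the other.
- Layout (a): every subject has placebo in one of the three periods, in rotation. Layout (b): separate placebo subjects, 1 in 4.

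**Layout (a), one value per subject-period.** Write the shift as +D/2 in one cohort and -D/2 in the other. By symmetry the pooled placebo and the periods are unbiased, and the dose effects are biased by +fD and -fD. In the positive cohort a subject's residuals are D/2 - fD (two active periods) and D/2 (placebo). With compound symmetry and correlation ρ, V⁻¹ is proportional to I - kJ, where k = ρ/(1 + 2ρ). Setting the score for an active dose to zero:

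1/2 - f - k(3/2 - 2f) = 0, so f = (1/2)(1 - 3k)/(1 - 2k) = (1 - ρ)/2.

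**Layout (a), four conditionally independent readings per period.** With per-reading ICC r, the period-mean ICC is ρ = 4r/(1 + 3r), so f = (1 - r)/[2(1 + 3r)]. For r = 0.4: ρ = 1.6/2.2 = 0.727 and f = 0.136.

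| ICC | f, ICC of period means | f, per-reading ICC, four readings |
|---|---|---|
| 0.2 | 0.40 | 0.25 |
| 0.4 | 0.30 | 0.14 |
| 0.6 | 0.20 | 0.07 |
| 0.8 | 0.10 | 0.03 |

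Direct matrix calculation with 12 per cohort gives the same values. Readings taken in one period probably share some occasion variance, which would put the truth between the two columns.

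**Size on the ratio scale.** For an assumed 20% cohort difference, D = ln 1.2 = 0.182.
- f = 0.30: exp(±0.0547) = 0.947 and 1.056, or about -5% and +6%.
- f = 0.136: exp(±0.0248) = 0.976 and 1.025, or about ±2.5%.

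**What makes it larger.** At per-reading ICC 0.3 and 0.5, complete data give f = 0.18 and 0.10. With 40% of samples missing at random, f is about 0.27 and 0.17. In layout (b), f = 0.50 at every ICC.

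**Pattern.** With alternate doses the signs along the ladder are -, +, -, +, -, +. If one cohort takes the three lowest doses and the other the three highest, they are -, -, -, +, +, +.

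**With a fixed cohort term** the bias is zero in all six contrasts. Standard errors for 12 per cohort, layout (a), total SD 1, four readings:

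| Per-reading ICC | As planned | Cohort added | Change |
|---|---|---|---|
| 0 | 0.323 | 0.339 | 5% |
| 0.3 | 0.307 | 0.312 | 1.6% |
| 0.5 | 0.266 | 0.268 | 0.7% |

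With one value per period the increase is 5.5% at ICC 0.2 and 1.0% at ICC 0.8. Coding period as six sessions also removes the bias, but the standard error at per-reading ICC 0.5 is then 0.307.

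**The case against.** - **The random subject effect already does most of the work.** This stands in part. With four conditionally independent readings it keeps out 75 to 97% of the shift at per-reading ICC 0.2 to 0.8. With period-mean ICC over the same range it keeps out 60 to 90%. The rest gets through.
- **No cohort difference is shown.** This stands. The study is single-site, PIP3 is scaled by PIP2 + PIP3 from the same sample, and nothing in the SAP says sputum is processed in cohort batches. Chance differences between cohorts are ordinary subject variance, which the model allows for. The bias arises only from a systematic shift.
- **The PK precedent is not a close match.** This also stands. The cohort terms in section 8.1.5.1 serve to compare dose slopes, there is no placebo contrast there, and the stated power-model equation has no cohort term. The precedent shows that cohort was considered for Part A, not that its absence here contradicts the plan.
- **Period might be coded as six sessions**, which would absorb cohort already. The SAP does not settle this; the synopsis describes 3-period cohorts.
- **Little depends on it.** PIP3 is exploratory, and section 3.1 bases dose decisions on safety and preliminary PK data. This stands and limits the weight of the point.

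A reader might also infer that the dose-response will show a false zig-zag. The SAP does not support that as a fact. Alternate dosing is the usual reading of interlocking cohorts, but the SAP nowhere states it, and the alternating sign depends on it.

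**Conclusion.** The omission is real and its direction is clear: any systematic cohort shift moves the two cohorts' placebo ratios in opposite directions. With complete data, one placebo period per subject and period coded 1 to 3, the fraction that leaks through is 0.4 to 0.1 at period-mean ICC 0.2 to 0.8, or about 0.25 to 0.03 at the same per-reading ICCs. It is larger with missing sputum samples, and one half with separate placebo subjects. The ICC, the cohort difference, the placebo layout and the dose allocation are assumptions. The point therefore identifies a small, avoidable vulnerability in an exploratory analysis. It does not demonstrate that the Part A PIP3 results are biased.

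**What to change.** In section 8.2.2, specify the Part A fixed effects as cohort, period and treatment*daytime, with subject random, and state that period is coded 1 to 3 in both cohorts. State the dose-to-cohort allocation and the placebo layout in the same place, so that a reader can see which contrasts share a cohort.

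The cost is one model term, one between-subject degree of freedom and, if every subject has a placebo period, about 0 to 6% wider standard errors. If placebo is given to separate subjects, the price is higher: the same calculation with 1 in 4 on placebo and four readings gives about 6 to 25% at per-reading ICC 0 to 0.8. The bias removed is also largest in that layout. Nesting period within cohort is not needed, because it costs more precision than a single cohort term when each subject has a placebo period.

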10.2. Appendix 2: Assessment Windows

10.2.1. Definitions of Assessment Windows for Analyses

Analysis Set / Domain	Parameter (if applicable)	Target	Analysis Window		Analysis Timepoint
			Beginning Timepoint	Ending Timepoint	
e.g. "Safety", "Efficacy" or list specific domains if required	e.g. "All" or list specific parameters (i.e. tests) if required	The target or most desired relative day or relative time value for a given visit. e.g. "Day 7"	e.g. "Day 1"	e.g. "Day 10"	e.g. VISIT 1
Pharmacodynamic	Sputum PIP data	Day -2 or Day -1 (Part B)	Predose		PREDOSE
		Day 1 3h (Parts A and B)	Day 1 2h45m	Day 1 3h15m	Day 1 3h
		Day 1 24h (Part A)	Day 1 22h30m	Day 1 25h30m	Day 1 24h
		Day12 3h (Part B)	Day 12 ¹ 2h45m	Day 12 ¹ 3h15m	Day 12 3h
		Day 12 24h (Part B)	Day 12 ¹ 22h30m	Day 12 ¹ 25h30m	Day 12 24h

NOTES :

- All other data will be summarised using the planned timepoint.

[1] Note that if subject is unable to provide a sputum sample on Day 12, then they may have another attempt on Day 13. If this happens then the Day 12 windowing timing will be relative to the Day 13 dose rather than the Day 12 dose.

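### Under the VC model and pooled variance of SAP 8.2.2, the Part B PIP3 analysis uses one pre-dose sputum sample as both response and covariate, which makes the post-dose 90% CIs versus placebo too narrow

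*SAP*

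**What the plan says.** SAP 8.2.2 models the log of the PIP3 peak area proportion. For Part B the fixed effects are given as "Part B: treatment*daytime*base", and daytime takes the values "Baseline', 'Day 1 3h', 'Day 1 24h', 'Day 12 3h', 'Day 12 24h". Baseline is therefore a level of the response.

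The covariate base is not defined in 8.2.2. SAP 10.4.2.1 supplies the meaning: "For all endpoints the baseline value will be the latest pre-dose assessment". The assessment windows in 10.2.1 give one pre-dose target for sputum, "Day -2 or Day -1 (Part B". The Part B schedule in 10.1.1.2 agrees, allowing a second attempt only if the first fails or is insufficient.

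On variance, 8.2.2 says "Repeated measures analysis based on the two replicates for each subject on each study day", "Replicates are to be modeled using VC (variance components) structure" and "Daytime and subject will be fitted as random effects". The results are then described as "Point estimates of the daytime differences versus placebo and their associated 90% CIs will be calculated (using the pooled estimate of variance". SAP 10.8.1 covers the same PIP3 endpoint but asks for an unstructured R matrix, with CSH or CS as possible alternatives if that does not converge.

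**The concern.** The Baseline rows have as their response the very sample that enters on the right-hand side as base. With base on the log scale, the model reproduces them almost or exactly. They then add observations with next to no residual to a variance that is pooled over all daytimes and used for the post-dose comparisons. The pooled variance falls although nothing has been learned about post-dose variability.

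At stake are the modelled repeat-dose PIP3 ratios to placebo, shown in Table 4.202 and Figure 4.202 with 90% CIs. The displayed posterior probabilities of a ratio below 1 would be overconfident in the same direction if they use the same variance. PIP3 is an exploratory endpoint (SAP 2.2), and the SAP attaches no decision rule to it.

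**Working it through.** **Inputs from the SAP.** Two replicates per sample; one Baseline sample; three post-dose samples in Part B (Day 1 3h, Day 12 3h and Day 12 24h, by 10.1.1.2 and 10.2.1); VC structure; pooled variance; 90% CIs. The SAP gives no PIP3 standard deviation and no Part B sample size, so there is no figure of its own to reproduce.

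**Step 1: closed form, no SD needed.** Take the expanded form, treatment*daytime plus daytime*log base, on replicate means with subject random and complete data. Every daytime then has its own intercepts and slope on the same subjects, so the Day 12 3h estimate uses the Day 12 3h rows only. Its SE is proportional to the square root of the estimated total variance (subject plus residual), which is the average of the residual variances over the daytimes in the model. Write s1, s2, s3 for the post-dose residual variances.

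- Without Baseline rows: (s1 + s2 + s3)/3
- With Baseline rows: (0 + s1 + s2 + s3)/4
- Variance ratio 3/4; SE ratio sqrt(3/4) = 0.866, which is 13% smaller
- Coverage of a nominal 90% CI: 2*Phi(1.645 x 0.866) - 1 = 0.846

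REML fits gave an SE ratio of 0.866 in every data set checked for this form, with the point estimate unchanged.

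**Step 2: both replicate rows, daytime within subject.** Assumed: 12 per arm, log SD 0.5, subject share of non-replicate variance 0.5, replicate variance 0.05. Mean estimated components for the expanded form, with half the replicate variance counted for a two-replicate mean:

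- With Baseline rows: 0.034 + 0.103 + 0.050/2 = 0.162
- Without: 0.067 + 0.123 + 0.050/2 = 0.215
- Ratio 0.162/0.215 = 0.753, square root 0.868

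The simulated mean SEs agree: 0.169/0.195 = 0.867. The empirical SD of the estimate was 0.194 in both fits, so the extra rows add no real precision.

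**Step 3: the term as written.** Taken literally, the quoted term has one common intercept and a separate base slope for each treatment-by-daytime cell. The Baseline rows are then fitted closely, though not always exactly. Because the intercept is shared, they also move the post-dose estimate slightly (mean log ratio -0.487 with them against -0.498 without, in one case with 9 active and 3 placebo).

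**Step 4: simulated coverage of the nominal 90% CI, log base.** Assumed for the first four rows: 9 active with 3 or 9 placebo. For the rows that give a CI width ratio, also log SDs of subject 0.2 to 0.4, sample 0.4 and replicate 0.15 to 0.4; mean log base -3; true log ratio -0.51; Day 12 3h. The last two rows use the step 2 assumptions.

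| Fixed effects | Rows and random effects | Without Baseline rows | With Baseline rows | Ratio, with/without |
|---|---|---|---|---|
| As written | Replicate means, subject | 90-91% | 86-89% | CI width 0.898-0.952 |
| As written, separate run | Replicate means, subject | 88-90% | 86-89% | CI 4-9% narrower |
| Expanded | Replicate means, subject | 90-91% | 84-86% | CI width 0.854-0.861 |
| Expanded, separate run | Replicate means, subject | 88-89% | 83-84% | SE 0.866 |
| Expanded | Both replicates, subject and subject-by-daytime | 90.7% | 86.2% | CI width 0.580/0.669 = 0.867 |
| As written | Both replicates, subject and subject-by-daytime | 90.5% | 85.2% | CI width 0.588/0.651 = 0.903 |

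The scale of base is not stated. With raw base in the term as written, the contrast was 81-83% with Baseline rows against 87-89% without, and the CIs were 11-14% narrower.

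**The case against.** The strongest reply is SAP 10.8.1. It names the PIP3 ratio and orders an unstructured R matrix, with CSH as one alternative. If that ran over daytimes, Baseline would have its own variance and the post-dose CIs could be largely protected. A reader might otherwise infer that the intervals are too narrow whatever covariance rule is used, and the SAP does not support that. What remains is that 8.2.2, the section specific to this model, asks for VC and a pooled variance. Section 10.8.1 does not say whether UN runs over daytimes or over replicates, and over replicates it would still pool over daytimes. A Baseline variance near zero may prevent convergence, and the CS fallback pools again. UN was not simulated.

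Second, the 13% figure belongs to an expanded model that the SAP does not write out. This stands: for the term as written the effect is smaller, and it is not purely one of interval width.

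Third, a reader might take much lower coverage as the effect of the double use. With daytime crossed with subject and both replicate rows analysed, coverage was 72-79%. The same model without Baseline rows already gave only 82-85%, because no term then carries sample-to-sample variance within a subject. Most of that shortfall is a separate random-effects question: 8.2.2 does not say whether daytime is nested in subject.

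Fourth, base is undefined in 8.2.2 and might mean something else. No other meaning is given, and 10.4.2.1 applies to all endpoints.

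Fifth, the endpoint is exploratory, 10.6.2 leaves the decision on PD analysis until the data have been reviewed, and model checks are planned. This limits the stakes. The residual plots in 10.8.1 might show the pattern, but the remedy offered there is transformation, which does not stop a value from being regressed on itself. No prior or threshold is stated for the posterior probabilities, so no decision error rate can be inferred.

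**Conclusion.** The point holds for the model that 8.2.2 specifies. One sample is both response and covariate, no section removes the duplicate rows, and under VC with a pooled variance the post-dose 90% CIs come out too narrow. The SE ratio of sqrt(3/4) needs no assumed SD, but it does need the expanded form, complete data and three post-dose daytimes. All simulated coverages and the size for the term as written depend on assumed SDs and sample sizes. The direction was the same in every setting run under the pooled VC model. This is worth correcting before database freeze, but it bears on no primary or secondary conclusion.

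**What to change.** Choose one of two forms for Part B:

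- Restrict the responses to Day 1 3h, Day 12 3h and Day 12 24h, and fit treatment*daytime cell means plus log base (or daytime*log base).
- Keep Baseline as a response level and drop base as a covariate.

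In either case, analyse the geometric mean of the two replicates with subject random, or keep both replicate rows and add a subject-by-daytime random effect. State one covariance rule in place of VC in 8.2.2 and UN in 10.8.1.

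Two separate minor corrections: write out the lower-order terms and the scale of base, and delete Day 1 24h from the Part B list, since the schedule (10.1.1.2), the windows (10.2.1) and Figure 5.201 (10.11.10) show no such Part B sample.

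The cost is the wording of one exploratory model. No new data are needed. In the simulated cases with log base and replicate means, taking out the Baseline rows widens the CIs by about 5 to 17% depending on the form (1/0.952 = 1.05; 1/0.854 = 1.17).

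### The Part B PIP3 model has no treatment-by-daytime term, so its ratio to placebo is tied to the value and zero point of baseline, which the SAP does not fix

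*SAP*

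**What the plan says.** SAP section 8.2.2 models the natural log of the PIP3 peak area proportion. It writes the fixed effects out separately for each part:

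- Part A: "Part A: period, treatment*daytime"
- Part B: "Part B: treatment*daytime*base"

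The Part B daytime levels are "Part B: 'Baseline', 'Day 1 3h', 'Day 1 24h', 'Day 12 3h', 'Day 12 24h", so baseline is a level of the response as well as part of the fixed effect. The random part reads "Daytime and subject will be fitted as random effects".

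Under Model Results Presentation, the same section asks this model for adjusted geometric means, ratios to placebo at each time point and Bayesian posterior probabilities: "Part B: Point estimates of the daytime differences versus placebo and their associated 90% CIs will be calculated".

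Section 10.4.2.1 says "For all endpoints the baseline value will be the latest pre-dose assessment". Neither place says whether base enters the model as a log, a raw or a centred value. Appendix 8 (section 10.8.1) deals with degrees of freedom, covariance structure and residual checks, and adds no fixed effect.

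**The concern.** The Part B comparison with placebo needs a mean for each treatment at each time. Part A has the term that provides it and Part B does not. The random daytime and subject effects are common to both arms, so they cannot carry a treatment difference at a given time. The only route left for a treatment effect is a difference in slopes on baseline, and that fixes the shape of the estimated effect before any data are seen.

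At stake are the Part B adjusted geometric means, ratios to placebo, 90% CIs and posterior probabilities, which are reported in Table 4.202 and Figure 4.202. A true fall in PIP3 would be understated on average. Two programmers could also obtain different ratios from the same data, because the answer depends on how base is coded and at what value the ratio is read.

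**Working it through.** The SAP gives no effect size, baseline distribution or group size for this analysis, so there is no planned figure to reproduce. All numerical inputs below are assumptions.

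**1. What the literal model implies.** At a given daytime, with shared intercept a and slopes b_D (drug) and b_P (placebo):

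- drug mean = a + b_D × base
- placebo mean = a + b_P × base
- log ratio = (b_D − b_P) × base

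A random daytime shift cancels in the difference. The log ratio is 0 at base = 0 and proportional to base elsewhere. Multiplying base by a constant divides the slopes by the same constant, so a change of units has no effect. Moving the zero point or transforming base does change the result.

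**2. Size when the true log ratio is a constant δ.** Let base have mean m and variance v, with equal arms and balanced baselines. Code treatment as s = ±1/2 and regress δs on s × base. The slope difference is δ × m/(m² + v). Read at base = m:

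estimated log ratio ≈ δ × m²/(m² + v) = δ/(1 + CV²), where CV = SD/mean of base as entered.

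**3. Numbers, with a true ratio of 0.70 (δ = ln 0.70 = −0.357).**

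| Base as entered (assumed) | Factor 1/(1 + CV²) | Ratio at mean base |
|---|---|---|
| log, mean −3, SD 0.3 | 0.990 | 0.703 |
| log, mean −3, SD 0.5 | 0.973 | 0.707 |
| log, mean −2, SD 0.5 | 0.941 | 0.715 |
| log, mean −1, SD 0.5 | 0.800 | 0.752 |
| raw, CV 40% | 0.862 | 0.735 |
| raw, CV 60% | 0.735 | 0.769 |
| centred (m = 0) | 0 | 1.000 |

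**4. Dependence on base.** For log base with mean −1 and SD 0.5, the slope difference is −0.357 × (−1)/1.25 = 0.285. The fitted ratio is exp(0.285 × −1.5) = 0.652 at one SD below the mean, 0.752 at the mean, and exp(0.285 × −0.5) = 0.867 at one SD above. The true ratio is 0.70 throughout.

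**5. Small-sample check, one time point.** With 9 v 9 subjects, residual SD 0.4 and 4,000 simulations per setting, the literal model gives:

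- log base, mean −3, SD 0.4: about 0.70
- log base, mean −1, SD 0.4: 0.73
- log base, mean −1, SD 0.6: 0.76
- raw base, CV 40% and 60%: 0.73 and 0.76 (a skewed raw base shifts a little less, about 0.72 to 0.75)
- centred base: 1.00

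Coverage of the 90% CI is about 86 to 88% in the settings with SD/mean of 60%, and 0% when base is centred. A model with treatment plus base gives 0.70 and about 90% coverage throughout.

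**6. Mixed-model check.** This used REML with 12 per arm, two replicates, within-subject SD 0.25, replicate SD 0.15, log-base SD 0.4 and 25 simulated trials per setting. A model with treatment × daytime and daytime × base gave 0.716 for Day 12 3h, identical for log and centred log base and for log-base mean −3 or −1 (Monte Carlo SE about 0.026 on the log scale). On the same data the literal model gave:

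- log base, mean −3: 0.722 to 0.725
- log base, mean −1: 0.766 to 0.768
- raw base: 0.753 to 0.758
- centred base: 1.000 with standard error 0

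Results were similar with or without the Baseline rows and under either reading of the random daytime effect (crossed or within subject). Multiplying base by 10 changed nothing.

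**The case against.** The best reply is that the line is shorthand or a slip, perhaps for treatment × daytime plus base. The SAP does name only the highest crossing elsewhere: section 8.1.6.2 lists just day × parameter. There, however, the crossing is of two factors and does supply the cell means. Section 8.1.5.1 lists cohort alongside cohort × log dose, so the plan can write out a lower-order term when it means one. The slip reading is plausible but cannot be shown. Equally, the SAP never calls base continuous. That is the natural reading of a measured proportion, but it remains a reading.

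Several limits on size stand:

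- The response is a log proportion. If base is on the same scale, uncentred and far from zero, the bias is negligible.
- A proportion cannot exceed 1. A normal log base with mean −1 and SD 0.6 puts 4.8% of baselines above 1, so the larger log-scale shifts come from awkward settings.
- The SAP does not mention centring. Ratios of exactly 1 with zero standard error would be noticed at quality control.

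A reader might infer that the Part B ratios will be materially biased. The documents do not support that, because they give neither the scale of base nor its distribution. Nor is the model shown to be over-parameterised. On the five listed daytimes it has 1 intercept + 10 slopes = 11 fixed parameters, and a model with 10 cell means + 1 slope also has 11.

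**Conclusion.** The specification is wrong as written. Read literally, it cannot return a ratio to placebo that is free of the zero point and value of base, and the SAP states neither the scale of base nor the value at which the ratio is read. That conclusion needs no numerical assumption, only that base is continuous.

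The size does rest on assumptions. It runs from negligible (0.70 to 0.715 for a true 0.70) with uncentred log base around −3 to −2, through about 0.73 to 0.76 on the raw scale with CV 40 to 60% or with log base nearer zero, to a complete loss of the effect if base is centred. The pull towards 1 is an average result under balanced baselines.

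Section 2.2 lists PIP3 as exploratory, and section 3.1 bases dose decisions on safety and PK. The consequence is confined to the Part B PIP3 model outputs: adjusted means, ratios, 90% CIs and posterior probabilities.

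**What to change.** For Part B in section 8.2.2:

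- Fit post-dose responses only: Day 1 3h, Day 12 3h and Day 12 24h. Drop Baseline as a response level, since it is also the covariate. Drop Day 1 24h, which Part B does not collect: the schedule in section 10.1.1.2 has only a 3h sample on Day 1, section 10.2.1 assigns Day 1 24h to Part A, and Figure 5.201 omits it.
- Use treatment × daytime plus the natural log of the baseline PIP3 proportion as fixed effects. Add daytime × base if the slope may differ by time.
- State the scale of base and whether it is centred. With treatment × daytime in the model and no treatment-by-base term, centring no longer affects the ratios.
- Take the drug/placebo ratios from the treatment × daytime least squares means.

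The cost is a few lines of SAP text and one model statement, settled before database freeze. On the three post-dose times the parameter count is the same as for the literal model: 6 cell means + 1 slope = 7, against 1 intercept + 6 slopes = 7. Time-specific slopes would make it 6 + 3 = 9. No extra data are needed.
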